1. PURPOSE OF STUDY

Aim 1: To examine the feasibility of the home-based transcranial direct-current stimulation (tDCS) apparatus and protocol (as well as the home-based tDCS sham protocol) for future use as an adjunctive treatment to prevent suicidal ideation (SI) relapse in adult patients with mood or bipolar disorders after discharge from the Comprehensive Psychiatric Emergency Program (CPEP) or inpatient unit to which they were admitted with SI or attempt.

Hypothesis 1: We expect at least 70% of the subjects to complete at least 5 of recommended 10 RS-tDCS sessions within three weeks of receiving the home-based tDCS device.

Aim 2: To detect a preliminary signal of the effect of adjunctive home-based tDCS on indices of SI measured with The Columbia-Suicide Severity Rating Scale (C-SSRS) in adult patients with mood or bipolar disorders after discharge from the CPEP or inpatient unit of which they were admitted with SI or attempt.

Hypothesis 2: Subjects in the active tDCS arm will report less suicide ideation intensity (as measured by C-SSRS) than subjects in the control (sham) group at the end of treatment, which will help to determine an effect size for use in the sample size calculation for a full randomized controlled trial.

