4. STUDY DESIGN

This is a single-center, randomized, sham-controlled, double-blind clinical study to investigate the feasibility of delivering RS-tDCS sessions for high-risk patients for suicide in the days following discharge from the CPEP or inpatient unit which they were admitted with SI or attempt. We plan to assess up to 80 adult patients for eligibility over 12 months of which 20 will be enrolled and randomized. Clinical assessments will be performed at baseline, post-treatment day 14 (14 days after the first RS-tDCS session), and follow-up day 30 and 60 (30 and 60 days after the first RS-tDCS session, respectively).

All study outcome measures are described in Table 1.

Time points		in-person	remote	
	Measures		S1 to S10	C14, C30, and C60
Eligibility screening		Х		
Informed consent		Х		
Enrollment		Х		
		Baseline		
Demographic data		Х		
General medical history		X		
Orientation tDCS session		X		
Loan agreement		Х		
	Feasibility		X*	
	C-SSRS	X		Х
	RRS	X		Х
	CAST	Х		Х
	MADRS	Х		Х
	C-SSRS SV		X	
	Side effects questionnaire		X	
	Treatment emergent event review		Х	Х
	Acceptability questionnaire		X**	
	Blinding assessment		X**	

Table 1. Study's time points and measures.

C14, C30, and C60: clinical assessments at post-treatment day 14, follow-up day 30 and follow-up day 60; CAST: The Concise Associated Symptoms Tracking; C-SSRS: The Columbia-Suicide Severity Rating Scale; C-SSRS SV: The Columbia-Suicide Severity Rating Scale – screening version; MADRS: Montgomery-Asberg Depression Rating Scale; RRS: Ruminative Responses Scale; S1 to S10: remotely supervised transcranial direct current stimulation (RS-tDCS) sessions one to ten.

*Number of completed RS-tDCS sessions per participant within three weeks of the study.

**applied only once, after the final RS-tDCS session (the tenth session).

Primary outcome measures:

Page 5 of 22 Version Date: 10/09/2023 1. Feasibility of the intervention – number of completed remotely supervised transcranial direct current stimulation (RS-tDCS) sessions, for both active and sham groups:

We expect at least 70% of the subjects to complete at least 5 of recommended 10 RS-tDCS sessions within three weeks of receiving the home-based tDCS device.

This criterion is based on a study that reported dropout rates between 22% and 25% of homebased tDCS for patients with bipolar depression (40) and that therapeutic effects with tDCS could be achieved within one week of treatment (24).

Secondary outcome measures:

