3. Proportion of patients who answered "no" for both questions 1 ("Have you wished you were dead or wished you could go to sleep and not wake up?") and 2 ("Have you actually had any thoughts of killing yourself?") of the C-SSRS (time frame: day 14 [+ 7 days], day 30 [+ 7 days], and day 60 [+ 10 days] from the first RS-tDCS session). This will help to determine the proportion of subjects who presented suicidal ideation relapse since the negative answer for both questions will be an inclusion criterion for this study.

4. Intensity of rumination as assessed by the Ruminative Responses Scale (RRS) (44) (time frame: day 14 [+ 7 days], day 30 [+ 7 days], and day 60 [+ 10 days] from the first RS-tDCS session):

The RRS encompasses 22 items. Each item is rated on a 4-point Likert scale: 1, almost never; 2, sometimes; 3, often; 4, almost always. The score on this scale is obtained by simply summing the scores on the 22 items.

5. Symptoms associated with suicidal ideation as assessed by the Concise Associated Symptoms

Tracking (CAST) scale (time frame: day 14 [+ 7 days], day 30 [+ 7 days], and day 60 [+ 10 days] from the first RS-tDCS session):

The 16 items of the CAST Scale assess symptoms across five domains: anxiety (three items, subscore range 3-15), irritability (five items, subscore range 5-25), mania (four items, subscore range 4-20), insomnia (two items, subscore range 2-10), and panic (two items, subscore range 2-10). The total CAST score ranges from 16 to 80. Each item is rated on a 5-point Likert scale: 1, strongly disagree; 2, disagree; 3, neither agree nor disagree; 4, agree; or 5, strongly agree, with higher scores indicating more severe symptoms.

6. Depressive symptoms as assessed by the Montgomery-Asberg Depression Rating Scale (MADRS) (time frame: day 14 [+ 7 days], day 30 [+ 7 days], and day 60 [+ 10 days] from the first RS-tDCS session):

MADRS is a 10-item questionnaire that includes questions on the following symptoms: 1. Apparent sadness 2. Reported sadness 3. Inner tension 4. Reduced sleep 5. Reduced appetite 6. Concentration difficulties 7. Lassitude 8. Inability to feel 9. Pessimistic thoughts 10. Suicidal thoughts. Each item yields a score of 0 to 6. The overall score ranges from 0 to 60. A higher MADRS score indicates more severe depression. The usual cutoff points are:

0 to 6 - normal/symptom absent; 7 to 19 - mild depression; 20 to 34 - moderate depression; >34 - severe depression.

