5. INCLUSION AND EXCLUSION CRITERIA

Inclusion criteria:

- age between 18 and 65 years

- diagnosis of mood or bipolar disorder registered in the electronic hospital medical record

- history of suicidal ideation and/or suicide behavior at the time of admission registered in the electronic hospital medical record

- absent of suicidal ideation at the time of enrollment (defined as questions 1 and 2 of the C-SSRS answered "no").

- ability and willingness to provide information and permission to contact at least one person in the case of a need to contact them to promote subject safety or inability to reach the subject for follow-up

- a living situation with access to a private space suitable for administration of the RS-tDCS sessions in next three weeks

- agree to use a medically acceptable form of birth control while receiving the treatment if you are an individual able to become pregnant

- living in Monroe County region, as this is the area covered by the Mobile Crisis Team, a URMC psychiatric emergency team serving anyone within Monroe County

- device or computer with internet access for a URMC-approved remote RS-tDCS supervision

- ability to manage proper use of the device in a practice session

Exclusion criteria:

- acute psychiatric instability or substance abuse (e.g., psychotic symptoms, alcohol misuse in the previous three months, use of any illicit drugs in the previous three months)

- unstable medical condition with reduction of functional capacity

- history of epilepsy or seizures in the last year

- history of neurodegenerative diseases registered in the electronic hospital medical record
- presence of or implanted any ferromagnetic metal in the head or the neck
- pregnant or breastfeeding or willingness to become pregnant in the next month

- history of head trauma (e.g., head injury, brain injury) or neurosurgery
- history of skin disorder or sensitive skin area near stimulation locations
- the presence of pacemaker
- current treatment with electroconvulsive therapy or transcranial magnetic stimulation

Although concurrent treatment with medications or psychotherapy is not an exclusion criterion, we will measure changes in medication and psychotherapy for descriptive and planning purposes (please, see "Secondary outcome measures", item 9).

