Research staff with training in using home-based tDCS by the Soterix Medical will meet with the subject via HIPAA-compliant videoconference previously scheduled. Subjects will be encouraged to find a distraction-free setting to complete treatment sessions. After guiding the subject with the proper adjustment of the SNAPstrap headgear and turning on the 1 x 1 Mini-CT device, research staff will provide the device unlock codes for one-time use to the subject. All ten device unlock codes for one-time use (one for each tDCS session) are obtained previously, just after the device is programmed to active or sham. The device unlock codes for one-time use allow the device to function only once a day, just after the inclusion of the code, with the level of electric current and duration of the session determined by the protocol, both (electric current level and duration of the session) pre-programmed on the device before it is delivered to the subject. Thus, the subject cannot alter the electric current level, the duration of the session, or use the device more than once a day. After each RS-tDCS session, research staff will apply the side effects questionnaire, review the subject's current treatment ("treatment review"), ask about any new or updated mental or physical symptoms since the last assessment (adverse events review), and apply the C-SSRS - screening version (C-SSRS SV) as part of the risk assessment (please, see more details on item "9. RISK TO SUBJECTS"). After the last RS-tDCS session (the tenth session), research staff will apply the feasibility questionnaire and blinding assessment. (Table 1). To assess blinding, the subjects will be asked the following question, "What treatment do you believe you have received??"(47). There will be three possible answers: 1) "active-tDCS"; 2)

"sham-tDCS" or 3) "Don't know". If the answer is "Don't know", research staff will ask "Would you be willing to provide your best guess about the treatment you received?", and could choose from two possible replies: 1) active-tDCS; 2) sham-tDCS (47, 48). We will use the Bang Blinding Index, which varies from -1 to +1, being 1 complete lack of blinding, +1 the opposite guessing, and 0 being related to perfect blinding (48). After the tenth session, the subject will be asked to send back the equipment in the pre-paid mail package to send it back.

Clinical assessments:

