- research staff will also communicate with the unit staff in case of any concerns about the subject during the baseline assessment.
- For this assessment, the following questions will be added, and the research staff must provide the answers ("yes" or "no"): "Active ideation with plan and intent *currently*?"; "Are you otherwise concerned about the patient at all?"

b) at the RS-tDCS sessions:

- after the C-SSRS screening version assessment, research staff will ask the subject if there is current active suicidal ideation with plan and intent. If the subject reports current active suicidal ideation plan and intent, research staff will inform the subject that they need to communicate this information (about the active suicidal ideation with specific plan and intent) to a licensed clinician from the research team to discuss the need for a specialized assessment.
- research staff will also communicate the licensed clinician in case of any concerns about the subject during the RS-tDCS sessions.
- For this assessment, the following questions will be added, and the research staff must provide the answers ("yes" or "no"): "Active ideation with plan and intent *currently*?"; "Are you otherwise concerned about the patient at all?"

c) at the clinical assessments (day 14, day 30, and day 60 from the first RS-tDCS session):

- after the C-SSRS assessment, research staff will ask the subject if there is current active suicidal ideation with plan and intent. If the subject reports current active suicidal ideation plan and intent, research staff will inform the subject that they need to communicate this information (about the active suicidal ideation with specific plan and intent) to a licensed clinician from the research team to discuss the need for a specialized assessment.
- research staff will also communicate the licensed clinician in case of any concerns about the subject during the follow-up assessments.
- For this assessment, the following questions will be added, and the research staff must provide the answers ("yes" or "no"): "Active ideation with plan and intent currently?"; "Are you otherwise concerned about the patient at all?"

The licensed clinician will follow the best policies and procedures of URMC and applicable state law for providing resources and determining if emergency evaluation is required. At minimum, the licensed clinician will:

- Advise the subject about emergency contact number

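### Secondary outcome 3 is meant to give the proportion who relapse, but it is defined only as three separate visit proportions, with no per-subject rule, no stated recall period and no use of the session screens

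*Combined protocol and SAP*

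**What the plan says.** Section 4, secondary outcome 3, is the proportion of patients who answer no to both of the first two C-SSRS questions, on the schedule "day 14 [+ 7 days], day 30 [+ 7 days], and day 60 [+ 10 days] from the first RS-tDCS session". Its purpose is given as follows: "This will help to determine the proportion of subjects who presented suicidal ideation relapse". The reason offered is that two negative answers are also required for entry, and section 5 describes that entry state as "absent of suicidal ideation at the time of enrollment".

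The second question is reproduced as "Have you actually had any thoughts of killing yourself", with no look-back period. None is stated elsewhere for the follow-up visits.

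Section 17 compares the groups at each time point with a t-test or chi-square test at 0.05. The sample of 20 is chosen for feasibility and is not derived from a relapse rate.

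After each stimulation session, section 8 has staff "apply the C-SSRS - screening version (C-SSRS SV) as part of the risk assessment". Table 1 lists this screen for sessions 1 to 10. No listed outcome or analysis uses the answers.

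Section 1 (Aim 1) describes the intended future use of the device "as an adjunctive treatment to prevent suicidal ideation (SI) relapse in adult patients".

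**The concern.** Subjects enter without ideation, so the proportion who presented relapse is a per-subject, ever-or-never quantity. The plan instead defines three marginal proportions and tests each one. Two consequences follow.

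- A subject who answers yes at day 14 and no at days 30 and 60 counts as relapse-free in two of the three results, and no result says how many subjects relapsed at all.
- A subject who answers yes at a session screen and no at the day 14 visit may count as relapse-free throughout, although study staff recorded the positive answer.

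The unstated recall period adds a further uncertainty. Without it, a reader cannot tell whether a *no* at day 60 covers the preceding month or only the day of the call. At stake is whether the trial can report the quantity that outcome 3 is said to serve.

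**Working it through.** The documents give no relapse rate, effect size or power for this outcome, so there is no figure to reproduce. The rates, recall periods and episode lengths below are assumptions, used to show ranges.

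**1. What separate visit proportions imply about ever relapsing.** Let p be the proportion positive at each of the three visits, with all visits attended.

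- Lower bound (the same subjects each time): p.
- Upper bound (different subjects each time): 3p, capped at 1.
- Independent visits: 1 − (1 − p)³.

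| Assumed p | Lower | Independent | Upper |
|---|---|---|---|
| 15% | 15% (3 of 20) | 1 − 0.85³ = 38.6% | 45% (9 of 20) |
| 20% | 20% (4 of 20) | 1 − 0.80³ = 48.8% | 60% (12 of 20) |

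Independence is not the upper limit. This ambiguity remains even if recall is complete.

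**2. Gaps between visits.** From section 4, the nominal gaps are 14 days (first session to day 14), 30 − 14 = 16 days and 60 − 30 = 30 days. With the visit windows they can reach 14 + 7 = 21 days, 37 − 14 = 23 days and 70 − 30 = 40 days.

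**3. What recall does to detection.** Visits are placed at days 14, 30 and 60. Session screens are placed on ten weekdays (days 1–5 and 8–12), since section 8 rules out weekend sessions. The missed share is for one 7-day episode with onset uniform over days 1–60.

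| Assumed recall | Days 1–60 covered, visits only | Days covered with ten screens | Missed, visits only | Missed with ten screens |
|---|---|---|---|---|
| 1 day | 3/60 (5%) | 13/60 (22%) | 65% | 53% |
| 7 days | 21/60 (35%) | 28/60 (47%) | 35% | 33% |
| 14 days | 42/60 (70%) | 42/60 (70%) | 17% | 17% |
| 30 days, or since last visit | 60/60 | 60/60 | 0% | 0% |

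For example, with 1-day recall and visits only, the episode is caught if it starts on days 8–14, 24–30 or 54–60. That is 21 of 60 onsets, so 39/60 = 65% are missed.

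The screens help only when recall is shorter than 14 days, and only in about the first two weeks. There the gain can be large: with 1-day recall and onset in days 1–14, the missed share falls from 50% to 0%. They add nothing between days 14 and 30 or between days 30 and 60.

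**4. What the text says about recall.** The evidence points both ways.

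- Section 5 uses the same two questions as a current-state criterion in people admitted with ideation or an attempt, which suggests short recall at entry. Where the protocol wants a look-back elsewhere (the treatment emergent event review in section 4, the adverse events review in section 8), it writes one.
- Section 9 adds a further step at the clinical assessments: "after the C-SSRS assessment, research staff will ask the subject if there is current active suicidal ideation with plan and intent". That would be partly redundant if the scale covered only the present moment.

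The recall period is therefore unspecified; it is not shown to be short.

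**The case against.** Several stronger readings are tempting, and the documents do not support them.

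- *The visits are point-prevalence snapshots, so recovered relapses are lost.* This is not established. The questions are phrased as looking back, and if they are asked since the last visit, no recovered episode is missed at attended visits. The loss is conditional on recall.
- *The visit data cannot be combined.* They can. Each subject's answers at all three visits are collected, so ever positive at a visit can be tabulated. What is missing is a stated rule.
- *Relapse by day 60 is the trial's main question.* It is not. Aim 1 is feasibility and refers to relapse prevention as a future use. Hypothesis 2 concerns ideation intensity at the end of treatment, and section 1 takes the effect size for a full trial from there. Relapse is one of eight secondary outcomes.
- *The ten session screens would close the gaps.* Ten is a maximum; the feasibility target reads "We expect at least 70% of the subjects to complete at least 5 of recommended 10 RS-tDCS sessions". The screens do not reach beyond the session period, and the documents do not list their items, so matching them to questions 1 and 2 is an assumption. Counting them also ties detection to attendance, which is post-randomisation, may differ by arm and may fall because of relapse.

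It is also fair that precision will be poor: 2 of 10 in one arm has an exact 95% interval of about 3% to 56%. These objections limit the point's weight and shape the remedy. They do not supply a per-subject definition or a recall period.

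**Conclusion.** The concern holds in limited form. Outcome 3 is said to inform the proportion of subjects who relapse, but as defined and tested it does not determine that proportion. At an assumed 15% positive per visit, the share who ever relapsed could be 15% to 45% (39% if independent); at 20%, it could be 20% to 60% (49% if independent). This part needs no assumption about recall, only about the visit rates.

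A second part is conditional. If recall is shorter than 14, 16 or 30 days (longer with the windows), episodes that resolve between visits are also missed. Under the assumptions shown, 65% of 7-day episodes are missed with 1-day recall and none with since-last-visit recall.

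The change is worth making because it is cheap and delivers the protocol's own stated quantity. Its weight is modest: a secondary outcome, about 10 subjects per arm, in a feasibility study.

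**What to change.** 1. Ask questions 1 and 2 at C14, C30 and C60 with reference to the period since the last clinical assessment. Say for C14 whether that runs from baseline or from the first session, since discharge and mailing of the device fall between them.
2. Define relapse per subject as any yes to question 1 or 2 at a clinical assessment through day 60, allowing for the visit window.
3. Report the cumulative proportion by arm at days 14, 30 and 60 with exact confidence intervals, and state how missed visits are handled.
4. Keep the per-visit proportions as description.
5. Add a sensitivity analysis that also counts positive answers on the corresponding items of the C-SSRS screening version, reported with the number of screens completed in each arm.

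The cost is wording in section 4 (outcome 3) and section 17, a recall instruction for interviewers, and use of data already collected. The drawback is that detection by session screen depends on sessions attended, which is why it belongs in a sensitivity analysis and not in the main definition. The arm-level estimates will remain imprecise and should be presented as such.

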7. The level of side effects will be assessed at the end of each session on a 0 (not at all) to 10 (highest degree) scale used by Ahn et al. (2019) (37), which includes the following symptoms: 1. Itching; 2. Burning; 3. Headache; 4. Fatigue; 5. Nervousness; 6. Dizziness; 7. Difficulty concentrating. The total score is the sum of the 7 items, varying from 0 to 70. Higher scores indicate higher levels of side effects.

8. Treatment emergent event review: after each RS-tDCS session and clinical assessment, subjects will be asked "Have you had any new symptoms, new medical conditions or been started on new medication/treatment since we last saw you?". This information will help research staff to judge about potential adverse events related to the trial. In addition, changes in treatment will help researchers to account for them in data analysis and the study's results interpretation.

4.1. **STUDY INTERVENTION**

The study intervention is tDCS treatments delivered by the Soterix Medical mini-CT device (https://soterixmedical.com/research/remote/mini-CT). The device is a nonsignificant risk (NSR) device study because it does not meet the definition of a significant risk device under §812.3 (m) of the investigational device exemptions (IDE) regulation (21 CFR §812)

(https://www.accessdata.fda.gov/scripts/cdrh/cfdocs/cfcfr/CFRSearch.cfm?fr=812.3).

The Soterix Medical mini-CT device for the RS-tDCS includes: (1) 1 x 1 mini-CT tDCS device; (2) SNAPstrap headgear, a "cap"-like placement for simple positioning and uniform electrode placement; (3) SNAPpads (individually-packaged pre-moistened sponge), and snap connectors (Figure 1) (39).

[figure not shown]

Figure 1. Remotely supervised (RS-tDCS) Equipment. (1) 1 x 1 mini-CT tDCS device; (2) SNAPstrap headgear: "cap"-like placement for simple positioning and uniform electrode placement; (2a) markers for guidance in placement; (2b) electrode polarity labeling with fixed wiring. (3) SNAPpad: (3a) individually-packaged pre-moistened sponge; perforated packaging for easy opening; (3b) snap connectors. (adapted from Pilloni, G., A. et al., Brain Stimul 15(3): 707-716, http://creativecommons.org/licenses/by-nc-nd/4.0/, DOI: 10.1016/j.brs.2022.04.014). The figure at the bottom simulates an RS-tDCS session.

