Subjects will be randomized 1:1 to either active or sham RS-tDCS. The active RS-tDCS delivers a constant current intensity of 2mA on the subject's scalp, with SNAPstrap headgear and 5x7 (35cm2) SNAPpads positioning bilaterally (anodal-left and cathodal-right), on the DLPFC, for 30 minutes. A similar protocol's administration was found effective, safe, and tolerable as an add-on intervention to decrease depressive symptoms in patients with bipolar depression (45). Sham tDCS looks identical to a typical RS-tDCS cap but delivers a 30-second ramp-up (0-2 mA) stimulation followed by a 30-second rampdown (2-0 mA) at the beginning and end of the application. Figure 2 shows a representation of the electric current delivered by the active and sham RS-tDCS.

[figure not shown]

Figure 2. Stimulation protocol. Active tDCS (upper) and sham tDCS (lower).

The tolerability and safety of home-based tDCS were assessed over 6,779 sessions from six clinical trials. Sessions were administered daily, with treatment ranging from 10 to 60 sessions per subject. The authors reported no serious adverse events, a similar proportion of tingling (68%), itching (41%), and warmth sensation (42%) between active and sham groups, and no participant discontinuation due to lack of tolerability (39).

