8. STUDY PROCEDURES

The pre-screening will be carried out through the electronic hospital medical record to identify potential subjects. Once the potential subject is identified, research staff will visit the unit where the patient is receiving treatment (inpatient unit or CPEP) and talk with unit staff in person, providing information about the study. Then, the research staff will ask unit staff to determine the most appropriate time for the research staff to meet with the patient based on knowledge of patient status and needs.

[figure not shown]
After screening and signing consent, the research study staff will collect demographic and general medical history data, apply the clinical questionnaires, and conduct the orientation tDCS session as part of the in-person baseline assessment (Table 1 and Figure 3). This demographic, general medical history, and clinical data will be collected and stored in the REDCap through a tablet or another portable electronic device. Per subject need/request, research study staff reads aloud instructions and questions while subjects hold the tablet to record their answers. If the REDCap site is down or malfunctioning, screening, consent, and questionnaires are completed on paper and later entered into REDCap.

The orientation session includes presenting the Soterix Medical mini-CT device to the subject to show how to turn it on/off, how to insert the device unlock codes for one-time use, how to correctly adjust the SNAPstrap headgear, and answer any questions they may have. As part of the orientation session, research staff will also conduct a 90-s tolerability test, with 2.0 mA as the starting point (electrical current intensity of the study protocol). During this test, the current intensity is ramped up to 2.0 mA and the subject will receive the stimulation for 90 seconds. The tolerability will be determined by subject rating below 7 on the 0-10 Visual Analogue Scale (VAS) of pain. If the subject finds the target tDCS dose intolerable (i.e., VAS 7 or higher), subjects will have the option of another test, with the amperage dose decreased by 0.5 mA (i.e., to 1.5 mA). If this lower amperage is also intolerable, the subject will be excluded from the study (39, 46). Thus, the orientation session aims to 1) familiarize the subject with the

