The tolerability and safety of home-based tDCS were assessed over 6,779 sessions from six clinical trials, with daily session, varying from 10 to 60 applications. The authors reported no serious adverse events, a similar proportion of tingling (68%), itching (41%), and warmth sensation (42%) between active and sham groups, and no participant discontinuation due to lack of tolerability (39). As described in "Study procedures," a tolerability test will be performed as part of the orientation session to verify if the subject can tolerate the electric current established in the protocol. Subjects will be informed that they can stop an RS-tDCS session anytime. During the RS-tDCS session, the stimulation will be stopped if the subject reports a sensation of pain rated as an intensity of 7 or above on a 1-10 scale (46). If the subject reports any event of critical concern related since the last RS-tDCS session, the next RS-tDCS session will not start until clear that the event is not stimulation-related. All devices function only after the inclusion of a unlock code for one-time use. The unlock codes for one-time use allow the device to function only once a day, just after the inclusion of the code, with the level of electric current and duration of the session determined by the protocol, both (electric current level and duration of the session) pre-programmed on the device before it is delivered to the subject.

Imminent risk of suicide, for the purposes of this study, refers to a subject who is currently 1) thinking about suicide; 2) preparing for suicide and/or having planned for suicide; and has 3) some intent to act on the suicide plan within the very near future (generally 48 hours).

This may differ for each case and therefore, clinical judgment along with timely consultation are needed for determination of imminence. Thus, to assess imminent risk of suicide, the following procedures will be undertaken:

a) at the baseline assessment in the hospital:

- after the C-SSRS assessment, research staff will ask the subject if there is current active suicidal ideation with plan and intent. If the subject reports current active suicidal ideation plan and intent at the baseline, research staff will inform the subject that they need to communicate this information (about the active suicidal ideation with specific plan and intent) to the unit staff in charge of the patient due to safety concerns.

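### The side-effect score leaves out tingling and warmth, mixes in illness-like symptoms and has no rating before stimulation, so it describes stimulation side effects only incompletely

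*Combined protocol and SAP*

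**What the plan says.** Section 4 (Study Design), secondary outcome 7, states: "The level of side effects will be assessed at the end of each session on a 0 (not at all) to 10 (highest degree) scale". The symptoms are "1. Itching; 2. Burning; 3. Headache; 4. Fatigue; 5. Nervousness; 6. Dizziness; 7. Difficulty concentrating", and the scoring rule is "The total score is the sum of the 7 items, varying from 0 to 70". The scale is taken from an earlier home-based tDCS study. Table 1 places it at sessions S1 to S10 only, with no entry at baseline.

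The tolerability evidence that the protocol cites is "a similar proportion of tingling (68%), itching (41%), and warmth sensation (42%) between active and sham groups". The same figures appear in section 2 (Background and Rationale), section 4.1 (Study Intervention) and section 9 (Risks to Subjects).

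Other provisions bear on the same question:
- Secondary outcome 8 asks an open question: "Have you had any new symptoms, new medical conditions or been started on new medication/treatment since we last saw you".
- Section 8 has a 90-second test before randomization: "The tolerability will be determined by subject rating below 7 on the 0-10 Visual Analogue Scale (VAS) of pain".
- Section 9 has an in-session criterion: "the stimulation will be stopped if the subject reports a sensation of pain rated as an intensity of 7 or above".
- Section 16 compares each adverse event between arms with Fisher's exact test.
- Section 8 assesses blinding by a treatment guess, summarized with the Bang index, once, after the tenth session.

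**The concern.** The protocol names three sensations as typical of this intervention, and its own instrument scores one of them. The most frequent, tingling, has no item. Warmth has none either, unless a subject chooses to score it as burning.

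Some of the items that are scored are not specific to stimulation. The MADRS includes "6. Concentration difficulties 7. Lassitude" and, as item 3, inner tension. These sit close to the side-effect items difficulty concentrating, fatigue and nervousness. Subjects have a mood or bipolar disorder, have recently been in hospital and may be on concurrent medication, so such symptoms may well be present before session 1. Without an earlier rating, they cannot be separated within a subject from effects of stimulation.

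What is at stake is the quality of the description. A low total could coexist with frequent tingling, and a raised total could reflect illness. Aim 1 covers the feasibility of the sham protocol as well as the active one, and item-level sensation ratings would help to interpret a Bang index away from zero. They matter more because the guess is taken only after the tenth session. A subject who stops after 5 to 9 sessions can count as a feasibility success but is never asked for a guess.

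**Working it through.** **The plan's own figure.** 7 items × 10 points = 70, which matches the stated range.

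**Coverage of the cited sensations.**

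| Cited sensation | Cited rate | Item in the score |
|---|---|---|
| Tingling | 68% | none |
| Warmth | 42% | none (burning is nearest) |
| Itching | 41% | itching |

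Two of three have no item of their own. If the rates were per subject, 0.68 × 20 = 13.6 subjects would be expected to have tingling and 0.42 × 20 = 8.4 to have warmth. The documents do not say whether the rates are per subject or per session, so these counts are conditional.

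**Share of the score that resembles illness.** Fatigue, nervousness and difficulty concentrating: 3 × 10 = 30 points, and 30/70 = 43%. If each stood at an assumed 2, 4 or 6 because of illness, they would add 6, 12 or 18 of the 70 points at every session. The documents give no such ratings.

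**What the missing pre-rating costs the arm comparison.** A total of 20 subjects randomized 1:1 gives 10 per arm. The standard error of a difference in baseline means is √(2/10) = 0.447 SD. The chance of an imbalance of at least 0.5 SD is 2 × [1 − Φ(0.5/0.447)] = 26%. With pre/post correlation r (assumed; none is given), covariate adjustment leaves 1 − r² of the variance, and a change score leaves 2(1 − r). The detectable standardized difference is (1.960 + 0.842) × √(2/10 × variance factor), for 80% power at two-sided 0.05 (sidedness is assumed).

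| r | Variance, covariate | Variance, change score | Detectable difference, covariate |
|---|---|---|---|
| unadjusted | 1.00 | – | 1.25 |
| 0.3 | 0.91 | 1.40 | 1.20 |
| 0.5 | 0.75 | 1.00 | 1.09 |
| 0.7 | 0.51 | 0.60 | 0.89 |

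The t-based unadjusted value is 1.33. At r = 0.3 a change score is noisier than the raw score; covariate adjustment is better than a change score at all three values.

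**What added items could show.** If both arms had the cited rate p, the 95% half-width for the active-sham difference is 1.96 × √(2p(1 − p)/10). This gives ±41 points for tingling (p = 0.68) and ±43 for warmth (0.42) or itching (0.41). The exact power of Fisher's test (two-sided, 0.05) for 68% against an assumed lower rate in the other arm is:

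| Other arm | 48% | 38% | 28% | 18% | 8% |
|---|---|---|---|---|---|
| Power | 5% | 12% | 24% | 43% | 69% |

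The added items would describe the sensations. They could not establish that sham matches active.

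**The case against.** The strongest reply is that this score does not carry tolerability alone. The pain ratings, the open question, the adverse-event comparison and session completion (the primary outcome) all bear on it, and blinding has its own measure. The study cited for the 68% tingling rate also reported that nobody stopped because of poor tolerability, so frequent tingling need not mean poor tolerability. Keeping a published scale unchanged is a legitimate choice, and no decision rule uses the total. Baseline MADRS and CAST partly cover the illness-like symptoms.

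Most of this stands, and it rules out three stronger readings that a reader might infer:
- *That the trial cannot show tolerability.* The other provisions contradict this.
- *That the score was meant to demonstrate sensory matching, or that the protocol predicts it.* Outcome 7 assigns no such purpose. The similar proportions are a cited study's result, not a hypothesis for this trial.
- *That the missing pre-rating biases the active-sham comparison.* Under 1:1 randomization, illness symptoms are balanced in expectation. The losses are precision, protection against chance imbalance, and within-subject attribution.

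The gap itself remains. The open question is unprompted and ungraded, and tingling that recurs at each session is no longer new. Both pain criteria use a threshold of 7 and score neither tingling nor warmth. The Fisher comparison sees only what is recorded as an adverse event.

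**Conclusion.** The point holds as a modest one. The total omits two of the three sensations that the protocol cites, including the commonest, and 43% of its range comes from items that resemble MADRS items, with no rating before stimulation. It is an incomplete and partly illness-confounded description of stimulation side effects and of active-sham similarity, and the documents support nothing stronger than that.

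The omission and the 30-of-70 share are read directly from the protocol. The expected counts, the illustrative symptom ratings, the pre/post correlations and the lower tingling rates are assumptions. Whether the source scale contains further items cannot be checked from the documents.

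**What to change.** Add tingling and warmth as two 0-10 items after each session. Report them separately, so that the 0-70 total stays comparable with its source. Report all nine items individually by arm with confidence intervals, labelled as descriptive.

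Optionally, take the full list once immediately before the first home session. The in-hospital baseline visit is less suitable, because discharge and mailing of the device come between it and session 1. Use this rating descriptively or as a baseline covariate, not as a change score.

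The cost is two questions per session, a REDCap form edit and, if the option is taken, one extra short questionnaire on a call that is already scheduled. The downside is slightly longer calls, and prompting for more sensations may raise reporting a little in both arms. Sensation ratings not collected at the session cannot be recovered later.
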